#### 6.2.1.3 Dose Limiting Toxicities (DLTs)

The DLT window (ie, DLT evaluable period) will start on Day 1 (start of the administration of the first infusion). The duration of the DLT window is 28 days from infusion Day 1.

The DLT window may also be extended to assess events starting within the window in case the DLT definition is time dependent.

See Section 3.4 for description of DLT evaluability and replacement of subjects.

All available safety data for subjects who are not DLT evaluable will still be evaluated and considered in DLRT recommendations.

A DLT will be defined as any of the events described below occurring in a subject during the DLT window unless clearly attributable to causes other than AMG 562 treatment. The CTCAE version 4.0 (see Appendix A) will be used to assess toxicities/adverse

events with the exception of CRS and tumor lysis syndrome (TLS). See Section 6.2.1.4 and Appendix K for grading criteria of CRS, neurotoxicity and TLS respectively.

- 1. Death not clearly due to the underlying disease or extraneous causes.
- 2. Any subject meeting the criteria for Hy's Law case (ie, severe drug-induced liver injury [DILI]) will be considered a DLT. A Hy's Law case is defined as: AST or ALT values of ≥ 3x ULN AND with serum total bilirubin (TBIL) level of > 2x ULN or INR > 1.5 without signs of cholestasis and with no other clear alternative reason to explain the observed liver-related laboratory abnormalities (see Section 6.4 for hepatotoxicity management and Appendix A for further explanation of Hy's law case and Management of Hepatic Function)
- 3. Non-hematologic DLTs:
  - Non-hematological adverse event grade 3 or higher, EXCEPT:
    - infection responding to antibiotic/anti-infective treatment within 48 hours
    - grade 3 fatigue or asthenia
    - grade 3 headache that improves to grade ≤ 2 within 72 hours
    - grade 3 insomnia that improves to grade  $\leq$  2 within 72 hours
    - grade 3 fever that improves to grade  $\leq$  2 within 72 hours
    - grade 3 nausea, vomiting or diarrhea responding if managed with optimal medical support and resolves within 72 hours
    - laboratory parameters of grade ≥ 3, not considered clinically relevant , and improved to grade ≤ 2 within 72 hours
- 4. Hematologic DLTs:
  - Febrile neutropenia grade 3 or higher unless responding to antibiotic/anti-infective treatment within 48 hours
  - Grade 4 neutropenia lasting more than 5 days
  - Grade 4 thrombocytopenia lasting more than 7 days

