  - Grade 3 thrombocytopenia with hemorrhage or required platelet transfusion
  - Grade 3 anemia with symptoms or required intervention (eg, transfusion)
  - Grade 4 anemia in the absence of detectable lymphoma as it may reflect a marrow toxic effect of AMG 562

Any adverse event, that meets the DLT definition, occurring outside the DLT evaluation period that is determined by the investigator to be possibly related to AMG 562, which is seen more frequently or is more severe than expected or is persistent despite appropriate management, can be determined to be a DLT upon unanimous decision by the DLRT after review of the adverse event and all available safety data.

An event should be considered related to treatment if, in the investigator's medical judgement, there is a reasonable possibility that the event may have been caused by AMG 562.

The dosing schedule is described by Part 1 Study Design and Schema and also in the protocol synopsis.

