# **Dose Limiting Toxicities**

Subject incidence of DLTs will be used to fit the BLRM model to estimate the probability of having a DLT across dose level. Adverse Events

Subject incidence of all treatment-emergent adverse events (TEAEs) will be tabulated by system organ class and preferred term. The number and percentage of subjects

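### The DLT list counts grade 3 thrombocytopenia with bleeding or transfusion but omits the same event at grade 4 if it lasts 7 days or less; the anemia bullets have a similar inversion

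*Protocol*

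**What the plan says.** Protocol Section 6.2.1.3 defines a DLT as any event on its list. Four hematologic bullets matter here:

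- Platelets: "Grade 4 thrombocytopenia lasting more than 7 days" and "Grade 3 thrombocytopenia with hemorrhage or required platelet transfusion".
- Red cells: "Grade 3 anemia with symptoms or required intervention (eg, transfusion" and "Grade 4 anemia in the absence of detectable lymphoma as it may reflect a marrow toxic effect of AMG 562".

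The same list shows how the protocol writes a threshold that includes higher grades: "Febrile neutropenia grade 3 or higher unless responding to antibiotic/anti-infective treatment within 48 hours". The non-hematologic item also starts at grade 3 or higher. A listed event counts if it occurs "during the DLT window unless clearly attributable to causes other than AMG 562 treatment". The DLRT may add late events, but that power covers "Any adverse event, that meets the DLT definition, occurring outside the DLT evaluation period".

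SAP Section 5 takes its DLT definition from this protocol section and adds no platelet or anemia rule. On use of the count, Protocol Section 10.5.2 states "Subject incidence of DLTs will be used to fit the BLRM model". Section 3.1 ends enrollment to a cohort once two or more subjects have a DLT at a dose level. Table 17 sets the expansion stopping boundaries in numbers of DLTs.

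**The concern.** A toxicity definition should not become more lenient as the event gets worse. If grade 3 thrombocytopenia that needs a platelet transfusion is dose limiting, grade 4 thrombocytopenia that needs one should be too. Under the list as written it is not, unless it lasts more than 7 days. A transfusion may itself lift the count out of grade 4 before day 7, so the intervention that makes the event important can also keep it under the duration limit.

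At stake is the DLT count in a first-in-human study whose primary endpoint includes DLT incidence. An omitted event does not reach the three rules that run on that count. Sites could also score the same event differently, some by the literal text and some by its presumed intent.

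**Working it through.** This is a question of rule logic, so the check applies the bullets literally to every combination.

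**1. Platelets** (the two platelet bullets)

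| Lasts > 7 days | Bleeding or transfusion | Grade 3 a DLT? | Grade 4 a DLT? |
|---|---|---|---|
| no | no | no | no |
| no | yes | **yes** | **no** |
| yes | no | no | yes |
| yes | yes | yes | yes |

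One cell is inverted.

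**2. What else on the list could catch that cell.** There is no hematologic catch-all. Three routes remain: the event met the grade 3 bullet before it worsened; the bleeding is itself a non-hematologic event of grade 3 or higher; or the subject died. The late-event power does not help, because it requires an event that already meets the definition. What is left is grade 4 for 7 days or less, with transfusion or with bleeding below grade 3, where the grade 3 criterion was not already met.

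**3. Anemia** (the two anemia bullets)

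| Symptoms or intervention | Lymphoma detectable | Grade 3 a DLT? | Grade 4 a DLT? |
|---|---|---|---|
| no | no | no | yes |
| no | yes | no | no |
| yes | no | yes | yes |
| yes | yes | **yes** | **no** |

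One cell is inverted here too, and it is the usual one. Inclusion 107 requires measurable disease (or PET positivity in dose exploration). The first on-treatment PET/CT is at week 5, about when the 28-day window closes. Few subjects could be shown free of lymphoma inside the window.

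**4. How the count acts in Table 17.** With the stated beta(0.66, 1.33) prior and k DLTs in n subjects, the posterior is Beta(0.66 + k, 1.33 + n − k). The rule stops when P(rate > 33%) exceeds 90%. This reproduces all nine boundaries (6, 8, 10, 12, 14, 16, 18, 20, 21). At n = 10:

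- k = 6: Beta(6.66, 5.33), P = 94.4%, stop.
- k = 5: Beta(5.66, 6.33), P = 83.8%, continue.

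Across the nine looks the posterior is 90.0–94.4% at the boundary and 83.8–89.3% one event below it. One uncounted event at a boundary therefore changes the decision. That holds for any count threshold: it shows the route by which an omission acts, not how often it would.

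**5. After the change.** With *or higher* in the platelet bullet, the inverted platelet cells fall from 1 to 0. Either anemia repair described in the fix takes the anemia cells from 1 to 0. No boundary, sample size or stated probability changes.

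**The case against.** The strongest case on the other side has four parts.

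- **Other safeguards remain.** Protocol Section 10.4.2 has the DLRT review every toxicity of grade 3 or higher that misses the DLT criteria, and lets it act on them. These events still trigger the switch to multiple-subject cohorts. They count toward the 2-fold limit on escalation and, if related, bar intra-subject escalation. The BLRM recommendation is only one input to the DLRT. This stands: a reader might infer that such events would be ignored, and the documents do not support that. What the safeguards do not do is put the event into the DLT count.
- **The anemia condition is deliberate.** The grade 4 bullet gives its reason, a possible marrow effect when no lymphoma explains the anemia. This also stands. A reader might infer that *grade 3 or higher* is the only correct repair for anemia. It would largely cancel the sponsor's condition, since grade 4 anemia with neither symptoms nor treatment would be unusual. The condition does not, however, explain why symptomatic grade 3 anemia counts whatever the lymphoma status.
- **No rate is given.** A reader might infer that the safety stop is badly weakened. Suppose, purely as an assumption, that 2, 5 or 10 points of a true 40% DLT rate went uncounted. The chance that Table 17 stops the study would fall from 56% (the Table 18 value) to 46%, 31% or 13%. The last case needs 10/40, a quarter of all DLTs, to fall in these two cells after the catches in step 2. Nothing in the documents supports such a share.
- **The study has ended early.** SAP Sections 1 and 7.2 say so, and SAP Section 10 drops the summary of toxicity interval and DLT probabilities. Rewording now would change little prospectively. This stands and limits the practical weight of the point.

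A reader might also infer that these subjects drop out of the DLT-evaluable set, because Table 6 calls for permanent discontinuation at grade 4. Section 6.2.1.4.4 limits that to grade 4 non-hematologic events. This is a separate conflict between discontinuation rules and does not strengthen the present point.

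**Conclusion.** The platelet bullets are wrong as written: the less severe event counts and the more severe one does not. The list's own use of *or higher* elsewhere makes it hard to read *Grade 3* as including grade 4. The anemia bullets show the same inversion while lymphoma is detectable, but which way to resolve it is a clinical decision for the sponsor.

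The defect is confined to the DLT count and the three rules that use it. Its numerical effect is unknown. The conclusion rests on a literal reading of Section 6.2.1.3 and assumes that no site guidance outside these documents tells investigators to score grade 4 events under the grade 3 bullets.

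**What to change.** 1. **Platelets.** Insert *or higher* after *Grade 3* in the bleeding-or-transfusion bullet and keep the 7-day grade 4 bullet as an additional trigger. Cost: two words, and slightly more events may count as DLTs.
2. **Anemia.** Make the two bullets consistent by one of two routes.
   - Use *grade 3 or higher* and leave disease-related anemia to the existing attribution clause. Inclusion 109 has neutrophil and platelet floors but no hemoglobin floor, so some disease-related anemia that is not clearly attributable elsewhere would count.
   - Apply the lymphoma condition to both grades. Symptomatic or treated grade 3 anemia would then stop counting in most subjects during the window.
3. **Reporting now.** In the DLT output, flag any grade 4 thrombocytopenia or anemia in the DLT window that was not scored as a DLT. SAP Section 9.6.2 already plans a listing of every adverse event, and that is the practical source: SAP Section 10 drops the listing of laboratory toxicities of grade 3 or higher. The cost is one flag on data already due for output.

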#### 6.2.1.4 Dosage Adjustments, Delays, Rules for Withholding or Restarting, Permanent Discontinuation

# 6.2.1.4.1 Infusion Interruptions/Delays/Withholding and Re-Start in Case of Technical/Logistical Issues

Events leading to infusion interruption or delay for technical/logistical reasons may include: technical problem with the infusion pump or the investigational product is incorrectly prepared or administered.

#### Infusion Interruptions due to Technical/Logistical Issues

The administration of AMG 562 should not be interrupted, if possible. In case of infusion interruption, due to any technical or logistic reason, the interruption should be as short as possible and the infusion continued at the earliest time possible.

In case of infusion interruption, immediately consult with Amgen Medical Monitor to determine if

- AMG 562 stability is sufficient to administer the remaining infusion or
- a new infusion can be administered or
- the dose should be withheld

If the remaining infusion can be administered, no specific precautions have to be taken. If a new infusion can be administered, follow the procedures in the schedule of assessments (Table 8 through Table 11) for the day on which the original (interrupted) infusion was administered. Premedication as described in Section 6.3 for the first infusion of the treatment should be administered. If the infusion will need to be withheld, follow the instructions for re-start after interruptions due to adverse events described below for the next infusion.

#### Infusion Delay due to Technical/Logistical Issues

If the infusion delay was up to 72 hours, the dose can be administered without specific precautions. Procedures performed will follow the schedule of assessments for the treatment day on which the infusion was originally planned. The following infusion should then be administered after 7 ( $\pm$  1) days; eg, if the Day 8 infusion needs to be

delayed for logistical issues, and could only be administered on Day 10, the next infusion should be administered on Day 17 ( $\pm$  1 day) rather than the regular Day 15. The  $\pm$  1 day window is allowed until the original dosing schedule is met again (in the example above, the third infusion could be administered on Day 16, and the fourth infusion on Day 22, if preferred for logistical reasons).

If the delay of the next infusion was > 72 hours, the dose will need to be skipped and the instructions for re-start after interruptions due to adverse events described below should be followed.

# Table 6. Infusion Interruptions/Delays/Withholding/Permanent Discontinuations and Management of Adverse Events Including Dose Reductions

	Interruption/ Delay	Specific Management	Re-start guidance	Permanent Discontinuation					
Infusion-related	ifusion-related Reaction (continued)								
Grade 3	Immediate interruption/ delay until event has improved to grade ≤ 1	Consider supportive therapy including steroids as clinically indicated. Increase monitoring of vital signs as medically indicated until the subject is deemed medically stable.	
 
As for grade 2 infusion-related reaction, with the exception of mandatory dose modification: reduce to next lower dose
 
	If subject missed more than 2 consecutive doses If recurrent grade 3					
Recurrent Grade 3 despite reduction of infusion rate & other measures	Immediate interruption	As for grade 3 infusion-related reaction	• n/a	Immediately stop the infusion (if applicable) and permanently discontinue AMG 562 therapy					
Grade 4	Immediate interruption	As for grade 3 infusion-related reaction	n/a	Immediately stop the infusion (if applicable) and permanently discontinue AMG 562 therapy					
Cytokine Releas	se Syndrome								
For Grading, Sto	or Grading, Stopping and Re-challenge Rules please refer to Table 7.								

Footnotes defined on last page of table

Page 2 of 5

Table 6. Infusion Interruptions/Delays/Withholding/Permanent Discontinuations and Management of Adverse Events Including
Dose Reductions

	Interruption/ Delay	Specific Management	Re-start guidance	Permanent Discontinuation
Any other adv	verse events including th	hose not meeting DL	.T criteria	
≥ Grade 3	Interruption/ delay required if deemed intolerable by the subject and not responding to appropriate medical management until event has improved to grade ≤ 1	n/a	
 
Re-start possible if successfully managed and improvement to ≤ grade 1 in ≤ 14 days.
 
In case of infusion interruption, continue treatment with next scheduled infusion, do not resume prior infusion or administer delayed infusion.
 
If next infusion is delayed:         
 
up to 72 hours: follow the schedule of assessments for the cycle day on which the infusion was originally planned. The following infusion should then be administered after 7 (± 1) days             

	If subject missed more than 2 consecutive doses In case of any event at grade 4

Footnotes defined on last page of table

Page 3 of 5

	Interruption/ Delay	Specific Management	Re-start guidance	Permanent Discontinuation
CNS grade 3	Interrupt AMG 562 immediately	Perform investigations per local practice including neuro exam, cerebral MRI and CSF analysis Dexamethasone should be administered at a dose of 3 x 8 mg /d over 3 days with step-wise dose reduction over up to 4 days	
 
Re-start possible within 2 weeks but not earlier than 3 days after infusion was stopped if successfully managed and improvement to ≤ grade 1 in ≤ 7 days.
 
Hospitalization: 72 hours
 
Dose modification: resume at the same dose or reduce to next lower dose if clinically indicated
 
Additional measures: premedication and additional assessments as indicated in Section 6.2.1.4.2.4 and Section 6.2.1.4.2.5 above.
 
	In case CNS event needed more than 7 days after treatment interruption to resolve to grade ≤ 1
CNS grade 4*	Interrupt AMG 562 immediately	As for grade 3 CNS-related event	n/a	Permanently discontinue AMG 562 therapy
Seizure grade ≤ 2*	Interrupt AMG 562, administer corticosteroids and antiseizure medication per local practice	n/a	
 
Do not re-initiate AMG 562 until 7 days after the last seizure and after therapeutic levels of antiseizure medication are likely to have been achieved
 
	Permanently discontinue if a 2 nd seizure occurs with re-initiation of AMG 562
Seizure grade ≥ 3 ∗	Interrupt AMG 562 immediately	Administer corticosteroids and antiseizure medication per local practice	n/a	Permanently discontinue AMG 562 therapy

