#### 3.4 Replacement of Subjects

Ineligible subjects (ie, subjects who were exposed to investigational product but post hoc were found to be ineligible) may be replaced.

Subjects enrolled in Part 1 may be replaced if they are not evaluable for DLT. Subjects will NOT be considered DLT evaluable if:

- the subject did not receive study treatment
- the subject missed 2 consecutive doses out of the 4 planned doses for reason(s) other than DLT during the DLT evaluation period
- the subject ended the study treatment before completion of DLT evaluation period for a reason other than experiencing a DLT.

Exception to this rule is:

Discontinuation of treatment due to early progression after receiving at least 3 doses of investigational product and safety follow-up data for entire DLT evaluation period are available.

All available safety data for subjects who are not DLT evaluable will still be evaluated and considered in DLRT recommendations.

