#### 6.2.1.4.2.2 Infusion Interruptions due to Adverse Events

Events occurring during the infusion and requiring treatment interruption will be managed by immediate infusion interruption. The site should record any unscheduled interruption of an infusion on the eCRF, and provide the start and stop date/time of the infusion.

Events requiring infusion interruption or permanent discontinuation are listed in Table 6.

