#### 6.2.1.4.3 Specific Guidance for Neurotoxicity

**Neurotoxicity** is a broad concept, including any adverse effect on the structure or function of the central and/or peripheral nervous system by a biological, chemical or physical agent. In this definition, neurotoxic effects may be permanent or reversible and result from direct or indirect actions on the nervous system (Erinoff, 'Interagency Committee on Neurotoxicology', 1995).

In case of grade 3 or grade 4 neurotoxicity events, perform investigations per local practice including neurological exam, cerebral MRI and CSF analysis after interruption of infusion.

Dexamethasone IV or PO should be administered at a dose of  $3 \times 8 \text{ mg}$  /d over 3 days with step-wise dose reduction over up to 4 days. For seizures  $\geq$  grade 2 administer corticosteroids and antiseizure medication per local practice.

Re-start of IP is possible within 2 weeks but not earlier than 3 days after infusion was stopped and if successfully managed with improvement to  $\leq$  grade 1 in  $\leq$  7 days. Subjects will remain hospitalized for 72 hours following re-start of IP. Following grade 2 seizure, do not re-initiate AMG 562 until 7 days after the last seizure and after therapeutic levels of antiseizure medication are likely to have been achieved.

#### 6.2.1.4.4 Permanent Discontinuation of AMG 562

AMG 562 treatment will be permanently discontinued in the event of:

- infusion-related reaction grade 4 (the infusion has to be stopped immediately, if applicable)
- recurrent grade 3 infusion-related reaction despite reduction of infusion rate & other symptomatic measures
- grade 4 CRS
- grade 2 or 3 CRS meeting any of the criteria listed below:
  - grade 2 or 3 CRS that does not improve to grade  $\leq$  1 within 7 days
  - grade 3 CRS that does not improve to grade  $\leq$  2 within 5 days
  - if a subject experiences 2 separate grade 2 or grade 3 CRS events regardless of dose
  - grade 3 CRS at the initial lower dose for treatment initiation (for cohorts with step-up dosing only)
- Occurrence of acute kidney injury considered related to AMG 562 by the investigator and meeting one or more of the following criteria:
  - Creatinine > 3x baseline or > 4.0 mg/dL and not recovered to CTCAE grade 1 or ≤ 0.3 mg/dL within 21 days
  - Hemodialysis required

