- DLT (separate guidance for CRS, IRR and Neurotoxicity) or other unmanageable toxicity unless a subject has a clear clinical benefit from treatment, the toxicity has resolved to grade ≤ 1 or baseline and after consultation with the sponsor
- in case of grade 4 non-hematologic adverse event
- grade 3 neurotoxicity needing more than 7 days after treatment interruption to resolve to grade ≤1
- Grade 4 neurotoxicity
- Grade ≥ 3 seizure
- In case of occurrence of more than one seizure of grade ≤ 2
- treatment interruption: if the subject misses at least 2 consecutive doses due to serious adverse events/adverse events
- possible DILI requiring permanent withholding as per Section 6.4
- subjects who require more than 1 dose reduction
- clinically relevant disease progression
- relapse of disease subsequent to response on protocol treatment
- occurrence or progression of a medical condition which in the opinion of the investigator should preclude further participation of the subject in the study
- administration of relevant non-permitted concomitant medications
- requirement for alternative therapy
- subject's request
- subject or investigator not compliant with the study protocol

For grading of events, refer to Section 9.2.2.1.

Females who become pregnant while on study through 120 days after receiving the last dose of study drug will not receive subsequent scheduled doses and will be followed for safety until the EOS visit.

Males with pregnant partners or whose partners become pregnant while the subject is on study through 180 days after receiving the last dose of study drug must practice sexual abstinence or use a condom while on study through 180 days after receiving the last dose of study drug.

All reasons for treatment discontinuation should be clearly and comprehensively documented in the eCRF. If a subject has not continued to present for study visits, the investigator should determine the reason and circumstances as completely and accurately as possible.

In any case of premature treatment discontinuation, the investigator should make every effort to perform all examinations scheduled for the EOT.

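### Table 6 and Section 6.2.1.4.4 give opposite stopping rules for a grade 4 cytopenia that is related to AMG 562 but is not a DLT

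*Protocol*

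**What the plan says.** **Table 6.** The row for other adverse events, which expressly takes in those that are not DLTs, covers grade 3 and above. Its permanent-discontinuation column reads "In case of any event at grade 4" and makes no exception for hematologic events. Section 6.2.1.4.2.2 gives the table binding force: "Events requiring infusion interruption or permanent discontinuation are listed in Table 6".

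**Section 6.2.1.4.4.** This list is also mandatory: "AMG 562 treatment will be permanently discontinued in the event of". Its general grade 4 entry is "in case of grade 4 non-hematologic adverse event". A separate entry covers "DLT (separate guidance for CRS, IRR and Neurotoxicity) or other unmanageable toxicity unless a subject has a clear clinical benefit from treatment". That waiver also requires resolution to grade 1 or baseline and consultation with the sponsor.

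**DLT definition (Section 6.2.1.3).** Duration decides whether these grade 4 cytopenias are DLTs: "Grade 4 neutropenia lasting more than 5 days" and "Grade 4 thrombocytopenia lasting more than 7 days".

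**DLT evaluability (Section 3.4).** A subject is not evaluable if "the subject ended the study treatment before completion of DLT evaluation period for a reason other than experiencing a DLT". The one exception is early progression after at least 3 doses with safety data for the whole window.

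**Table 6, row for events not related to AMG 562.** At grade 4 this row allows re-start, names neutropenia and thrombocytopenia as exceptions to its interruption rule, and stops treatment for good only if the same event recurs at grade 4 or more than 2 consecutive doses are missed.

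**The concern.** A short grade 4 neutropenia or thrombocytopenia attributed to study drug is not a DLT. An investigator who opens Table 6 must end treatment. One who opens Section 6.2.1.4.4 finds that neither the grade 4 entry nor the DLT entry applies. Two sites could handle identical subjects differently, and both could claim to follow the protocol.

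The first consequence is exposure: whether the subject receives further drug. The second is statistical. Section 3.4 ties DLT evaluability to whether treatment was ended early for a non-DLT reason, so the choice of page can decide whether the subject enters the DLT Analysis Set and the BLRM. Neutropenia is one of the important potential risks in Section 2.3, so the case is foreseeable.

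**Working it through.** No arithmetic is needed to establish the conflict; the passages are compared case by case. One reading is assumed: because Table 6 gives unrelated events their own row, the row for other adverse events is taken to govern related ones.

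| Grade 4 cytopenia | Table 6 | Section 6.2.1.4.4 | Result |
|---|---|---|---|
| Related, not a DLT (neutropenia ≤ 5 days, thrombocytopenia ≤ 7 days) | Stop permanently | Neither the grade 4 nor the DLT entry applies | Conflict |
| Related, DLT | Stop permanently | Stop, subject to the waiver | Differ only where the waiver would be used |
| Unrelated, first occurrence | Re-start allowed | No grade 4 trigger | No conflict |

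Lymphopenia belongs in the first line if it is recorded as a related grade 4 adverse event. Section 3.1 counts it as hematologic, and it is not on the hematologic DLT list. Section 9.2.2.1 limits how often it would be recorded, since laboratory findings without clinical significance are generally not adverse events.

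The unrelated-event row matters to the reconciliation for another reason. The grade 4 entry in Section 6.2.1.4.4 does not mention relatedness. An unrelated grade 4 non-hematologic event may therefore re-start under Table 6 but is stopped under Section 6.2.1.4.4.

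**Effect on the DLT data, first line of the table.** Take a cohort of 3 in which nobody has a DLT and one subject has a 4-day related grade 4 neutropenia in the window.

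- Section 6.2.1.4.4 applied, subject completes the window: 0 DLTs in 3 evaluable.
- Table 6 applied: 3 − 1 = 2 evaluable, so 0 DLTs in 2. If a replacement is enrolled, the third observation comes from a different subject.

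In a cohort of 4 the comparison is 0 in 4 against 0 in 3. One subject is thus 1/3 (33%) or 1/4 (25%) of the cohort.

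These are the two ends, not the only outcomes. A subject kept on treatment can still become non-evaluable by missing 2 consecutive doses of the 4 planned (Section 3.4). In a single-subject cohort, a delay of more than 7 days is enough (Section 6.2.1.4.2.3). Replacement is permitted, not required.

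**Does anything settle which passage governs?** No provision ranks Table 6 against Section 6.2.1.4.4, and the SAP has no rule on it. SAP Section 6.4 refers to Protocol Section 6.2.1.3 for evaluability, which refers on to Section 3.4. The SAP therefore inherits the question.

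**The case against.** The best defence is that the lists are cumulative. Section 6.2.1.4.4 does not claim to be exhaustive, so a site could apply it together with Table 6 and stop whenever either says so. That is workable, but it leaves the word non-hematologic with no function: if every related grade 4 event stops treatment anyway, there is nothing to restrict. The reading softens the contradiction without removing it.

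Other parts of the defence stand, and they rule out stronger readings that a reader might infer:

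- **That Table 6 stops every grade 4 event.** The wording belongs to one row. Unrelated events have their own row, which allows re-start.
- **That Section 6.2.1.4.4 exempts hematologic events.** Its DLT entry reaches grade 4 cytopenias that qualify as DLTs.
- **That the plan is silent on the DLT set.** Section 3.4 already classifies a subject who ends treatment early for a non-DLT reason. It also keeps that subject's safety data in the DLRT's deliberations.
- **That grade 4 cytopenia is expected at a known frequency.** The 20%-or-more category in Sections 2.2.4 and 2.3 describes common reactions to blinatumomab, including neutropenia. It is not a grade 4 rate and not for this drug. Section 2.3 mentions life-threatening cases without a frequency.
- **That response follow-up is lost on discontinuation.** The schedule footnotes require PET/CT 14 (+3) days after the last dose, and Section 7.2.4 follows disease status every 6 weeks until progression.

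The practical reach is also limited. SAP Section 1 reports that the study was discontinued early, and SAP Section 7.2 refers to one ongoing subject at the primary snapshot.

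**Conclusion.** The inconsistency is real but narrow. It is a direct conflict for AMG 562-related grade 4 cytopenia that is not a DLT, and a partial one for related grade 4 cytopenia that is a DLT, where only the waiver separates the passages. Within the DLT window, each affected subject may be lost from, or retained in, the evaluable set of a 3-to-4-subject cohort. How many subjects that involves cannot be estimated from the documents.

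The conclusion rests on both passages being binding, as their own wording indicates, and on the row for other adverse events governing related events. It is a wording inconsistency with a consequence for the dose-finding data, not a flaw in the BLRM or in the DLT definition.

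**What to change.** The sponsor should reconcile the Table 6 row for other adverse events with the grade 4 entry in Section 6.2.1.4.4, and both with the Table 6 row for unrelated events. The text should say whether hematologic grade 4 events trigger permanent discontinuation, so that a single rule applies wherever a site looks. No position is taken here on which clinical rule is right. No new rule for the DLT Analysis Set is needed, because Section 3.4 already covers it.

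The cost is amendment wording only: no new data, analyses or sample size. Since the study has been discontinued, the useful remaining step is to record in the study report which rule was applied to any subject with a related, non-DLT grade 4 cytopenia, and how that subject was classified for DLT evaluability.
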